12.0 Procedures Involved*

12.1 Provide a description of **all research procedures or activities** being performed and when they are performed once a subject is screened and determined to be eligible. Provide as much detail as possible.

NOTE: This should serve as a blueprint for your study and include enough detail so that another investigator could pick up your protocol and replicate the research. For studies that have multiple or complex visits or procedures, consider the addition of a schedule of events table in in your response.

Response:

All procedures will be performed on the same day as screening and consent and are expected to take 30-60 minutes. An annotated pain map of the vulva will be created based on subjective assessment of pain, and thermographic imaging.

- A. Images and Thermographic readings will be taken with an infrared camera prior to any physical contact with the vulva of the patient other than by placing a calibrated paper drape circumferentially on the vulva outside of the area of interest. The drape will be calibrated to maintain pain map/image size comparison between patients.
- B. Subjective pain at several predetermined loci will be assessed with a cotton swab (standard of care) and rated on a Likert scale of 0-10. This data will be added to the thermographic map.
- C. Comparative analysis of the two measures will be performed (separate from visit). Patient demographic and health data (see table below) will be collected by direct participant interview and review of the patient's chart in Allscripts.

12.2 Describe what data will be collected.

NOTE: For studies with multiple data collection points or long-term follow up, consider the addition of a schedule or table in your response.

Response:

Patient Name

DOB

MR#

Date of Visit

Vulvar images, both plain and infrared.

Pain sensitivity data on a Likert scale of 0-10 using cotton-tipped swabs.

Status (PWD or Control)

Race

Gravida

Para

Vaginal Births

Cesarean Births

Sexually Active

Dyspareunia

Smoking

Marital Status

Education Level

Medical History

Depression

Anxiety

Fibromyalgia

Chronic Pelvic Pain

Interstitial Cystitis

Endometriosis

Irritable Bowel Syndrome

TMJ

Other

h/o yeast infections

h/o BV

h/o abuse

PWD Patients Only

Symptom Duration

Pain Map Score

Pain Diary Score

FSDS

Previous Rx (Y/N)

Previous Rx (type)

 *12.3 List any instruments or measurement tools used to collect data (e.g. questionnaire, interview guide, validated instrument, data collection form).*

Include copies of these documents with your submission.

Response: Please see the attached data collection form.

12.4 Describe any source records that will be used to collect data about subjects (e.g. school records, electronic medical records).

Response: Electronic medical records (Allscripts) will be accessed to obtain information for the data collection form only if the patient-provided information is incomplete or unclear.

*12.5 Indicate whether or not **individual** subject results, such as results of investigational diagnostic tests, genetic tests, or incidental findings will be shared with subjects or others (e.g., the subject's primary care physician) and if so, describe how these will be shared.*

Response: No

*12.6 Indicate whether or not **study** results will be shared with subjects or others, and if so, describe how these will be shared.*

Response: No, although study results of de-identified data may be presented or published in a scientific context.

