1.0 Study Summary

Study Title	Objective Assessment of Pain Thresholds in Women with Vulvodynia
Study Design	Clinical Trial
Primary Objective	Develop annotated pain maps showing region and size of area sensitive to mechanical stimulus. The pain maps will be created by combining IR images, photographs, and clinical input, and will be correlated with patient co-morbidities.
Secondary Objective(s)	a-Determine changes in the location and size of sensitive regions following various conventional clinical interventions for vulvodynia. b-Develop a large, information-rich database of annotated pain maps from patients, and use Artificial Intelligence to identify patterns and trends.
Research Intervention(s)/ Investigational Agent(s)	Infrared imaging of the vulva and assessment of pain intensity using cotton-tipped swab.
IND/IDE #	N/A
Study Population	Women with vulvodynia and healthy controls
Sample Size	60 women (30 in each group)
Study Duration for individual participants	One day 1 hour

Study Specific Abbreviations/ Definitions	
--	--

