2.0 Objectives*

2.1 *Describe the purpose, specific aims, or objectives of this research.*

Response:

We have been developing a novel medical technique for the diagnosis and classification of vulvodynia. The technique will quantitatively quantify the magnitude and location of areas of sensitivity to touch/pressure and simultaneously use thermal and photo imaging to identify regions of inflammation. The technique builds on current methodology used in assessment and knowledge about the known pathophysiology of the disorder. For this aspect of study, we will assess thermal indicators of inflammation with an infrared camera and subjective pain sensitivity with traditional methods. Through this combination of measurements, we plan to expand the diagnostic tools used in patient care as well as on the classification of this heterogeneous disorder. Specific aims include developing annotated pain maps that show regions of sensitivity and changes in temperature; determining changes in the above parameters during and after traditional medical treatment for the condition; and developing a large database of annotated pain maps for use with artificial intelligence to identify patterns and trends which will be correlated with clinical outcome data.

2.2 *State the hypotheses to be tested, if applicable.*

NOTE: A hypothesis is a specific, testable prediction about what you expect to happen in your study that corresponds with your above listed objectives.

Response:

Women with vulvodynia will show specific patterns of pain sensitivity and inflammatory changes (identified by thermography) compared to women without vulvar pain.

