Vulvodynia is a heterogeneous group of clinical conditions defined by the [International Society for the Study of Vulvovaginal Disease](#) as chronic vulvar discomfort or pain, characterized by burning, stinging, irritation or rawness of the female genitalia [1]. The true prevalence is unknown but is estimated at 9-12% of the adult female population, with up to 2 million women affected. These chronic conditions cause significant burden in terms of quality of life and relationship dysfunction, especially for women with provoked vestibulodynia (pain at the opening of the vagina (“vestibule”) with vaginal penetration or attempted vaginal penetration) which interferes with normal sexual function [2]. This is a “hidden” women’s issue that is under-reported and under-treated because it causes embarrassment and feelings of inadequacy. The clinical management of localized, provoked vulvodynia has been disorganized and somewhat arbitrary [3]. Studies suggest that most women see a variety of providers over the course of months to years before the condition is diagnosed correctly. Diagnosis of these conditions is based on clinical picture, absence of other causes, and physical exam. During the exam, a cotton-tipped swab is used to assess for areas of tenderness and the patient is asked to rate her level of pain on a Likert scale. This has been the standard of care for many years, but reproducibility has not been assessed. In addition, monitoring response to therapy is also very subjective. Even return to sexual activity is not a reliable indicator of patient’s pain, since many women will continue to engage in sexual activity to avoid relationship discord. We have been developing a novel medical technique for the diagnosis and classification of vulvodynia. The technique will quantitatively measure mechanical sensitivity to touch/pressure simultaneously with thermal indicators of inflammation. The technique builds on current methodology used in assessment and knowledge about the known pathophysiology of the disorder. Through this combination of measurements, we plan to expand the diagnostic tools used in patient care as well as on the classification of this heterogeneous disorder.

4.2 *Include complete citations or references.*

Response:

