16.4 Describe your process to ensure that all persons assisting with the research are adequately informed about the protocol, the research procedures, and their duties and functions.

Response:

The study team has regular meetings to discuss and design the research project. All investigators are CITI trained. Only the PI, [name], and the study coordinator, will have direct contact with the study patients.

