19.0 Data Management and Analysis*

19.1 *Describe the data analysis plan, including any statistical procedures. This section applies to both quantitative and qualitative analysis.*

Response: Both visible and infrared images will be acquired using our state-of-the-art FLIR E-95 camera. The E-95 is one of the best IR cameras available. It has very high spatial resolution and temperature sensitivity. In summation: if there is any correlation between temperature and vulvodynia, this camera will be able to see it. The camera's software stores both of these images along with metadata in a single jpeg. We have already designed our own custom software to extract the raw temperature data from these files. Our software will control the camera remotely through a USB link. This, along with mounting the camera on a tripod, will ensure that there is minimal "smearing" of the image due to small uncontrollable movements of the person operating the camera. This will give us the highest accuracy possible. In addition, our graphical software interface will allow the user to mark the image to indicate where sensitivity to pressure or an increase in thermal activity was observed. As we expect spatial variation in temperature from the affected area to the unaffected, we will provide the user with a variety of options for subtracting the average body temperature to make the difference more visible. All data will be stored securely to maintain patient confidentiality. Once we have collected enough data, we can begin the process of establishing the metrics by which we can diagnose the patients. Considering all of our data (pressure, temperature, color (from visible light image)) we can determine the connection of each to a positive diagnosis and assign a finally probability to our result.

19.2 *If applicable, provide a power analysis.*

NOTE: This may not apply to certain types of studies, including chart/records reviews, survey studies, or observational studies. This question is asked to elicit whether the investigator has an adequate sample size to achieve the study objectives and justify a conclusion.

Response: This is a pilot study. No power analysis will be performed.

19.3 *Describe any procedures that will be used for quality control of collected data.*

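### The title, 4.1 and 19.1 promise objective pain thresholds and pressure data, but the only mechanical measure is a subjective 0-10 rating to a swab of unrecorded force, so no threshold or pressure value can be reported.

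*Combined protocol and SAP*

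**What the plan says.** **What is promised.** The study title in 1.0 is "Objective Assessment of Pain Thresholds in Women with Vulvodynia". The primary objective is to "Develop annotated pain maps showing region and size of area sensitive to mechanical stimulus". Section 2.1 says the technique will "quantify the magnitude and location of areas of sensitivity to touch/pressure", and 4.1 describes it as a quantitative measure of mechanical sensitivity. Section 19.1 builds a diagnostic probability from several inputs: "Considering all of our data (pressure, temperature, color (from visible light image".

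**What is done.** Section 12.1 B: "Subjective pain at several predetermined loci will be assessed with a cotton swab (standard of care) and rated on a Likert scale of 0-10". In the 12.2 data list the only mechanical entry is this swab rating.

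**What is conceded.** Section 2.1 says that this part of the study assesses "subjective pain sensitivity with traditional methods". Sections 6.1 and 12.1 also use the word subjective. Of the swab test, 4.1 says: "This has been the standard of care for many years, but reproducibility has not been assessed".

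**Who does it.** Section 16.4 restricts contact to the PI, a redacted name "and the study coordinator, will have direct contact with the study patients". It does not say who applies the swab.

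**The concern.** A pain threshold is the stimulus level at which pain begins. It needs a measured stimulus, and so does a pressure variable. A rating to a hand-held swab gives neither: a score of 6 could reflect a sensitive site touched lightly or a less sensitive site pressed hard.

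Two things are at stake. First, a report written to match the title or 19.1 would claim quantities that the data set does not hold. Second, the endpoint in 3.1 concerns thermographic change in the areas of pain sensitivity, and the swab rating is what marks those areas. If cases and controls were tested by different people, or with a different technique, the marking could be biased. Random variation in force would weaken any observed link between temperature and pain, and the data could not show whether a weak link reflects swab error or a true absence.

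**Working it through.** **Step 1. Trace the measure from title to analysis.**

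| Place | Term used | Is a matching quantity collected (12.1 B, 12.2)? |
|---|---|---|
| 1.0, title | objective, thresholds | No: no measured or graded stimulus and no threshold rule |
| 2.1 | magnitude of sensitivity to touch or pressure | Only as a 0-10 rating |
| 4.1 | quantitative mechanical sensitivity | Only as a 0-10 rating |
| 6.1 | subjective pressure sensitivity | Yes: the 0-10 rating |
| 12.1 B, 12.2 | subjective pain, 0-10 | Yes: this is the measure |
| 19.1 | pressure, as a diagnostic input | No force or pressure field |

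No section gives an applied force, a force-measuring device, a contact time, the number of applications per locus, the examiner or a repeatability check. The Pain Map Score, Pain Diary Score and FSDS in 12.2 are listed for affected women only and are not described as force or threshold measures.

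**Step 2. The plan's own figures.** There is no figure to reproduce beyond 30 + 30 = 60. Section 19.2 declines a power analysis because this is a pilot, and no reliability value is given. The next two steps are therefore illustrations on assumed inputs.

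**Step 3. Random error.** Let R be the reliability of a locus rating. With random error independent of true sensitivity, and temperature taken as error-free, observed correlation = true correlation × √R.

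| Assumed R | √R | A true correlation of 0.50 appears as |
|---|---|---|
| 0.5 | 0.71 | 0.35 |
| 0.7 | 0.84 | 0.42 |
| 0.9 | 0.95 | 0.47 |

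**Step 4. Systematic error between groups.** Take a locus at which cases and controls do not truly differ, and suppose that technique shifts one group's mean rating by b standard deviations. With 30 per group and a two-sided 5% z-test, the test statistic is centred at b / √(2/30) = b / 0.258.

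| Assumed b | Centre | False-positive rate |
|---|---|---|
| 0 | 0 | 0.05 |
| 0.1 | 0.39 | 0.07 |
| 0.2 | 0.77 | 0.12 |
| 0.3 | 1.16 | 0.21 |
| 0.5 | 1.94 | 0.49 |

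The plan names no such test, and nothing in the documents shows that b differs from zero. The table shows only that a modest difference in technique would matter at this sample size.

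**The case against.** The best defence is that the protocol is open about the measure. Sections 2.1, 6.1 and 12.1 all call it subjective, and 2.1 separates this stage from the wider technique that 4.1 describes. In 19.1, *pressure* can be read as shorthand, because the same section speaks of marking where sensitivity to pressure was observed. This stands: the fault is inconsistency of labels, not concealment. It does not rescue the title, and it is a reason to correct the word in 19.1 rather than leave it to be interpreted.

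Several stronger readings are tempting but not supported:

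- *Each locus is rated once.* The documents specify one visit but do not say how often each locus is touched. The data collection form mentioned in 12.3 is not available to settle it.
- *Several people apply the swab.* Section 16.4 limits patient contact and says nothing about who does the swab test. The fair criticism is that the examiner is unspecified.
- *The rating simply reflects the examiner's force.* Force is one component of the rating; its share cannot be computed from the documents.
- *The swab disturbs the thermography.* Under 12.1 A, images precede any contact with the vulva other than placing the drape. Swab error can affect which areas are labelled sensitive, but not their temperature.

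It is also fair to say that the figures in the working are hypothetical. Section 12.1 C promises only a comparative analysis, with no correlation coefficient named.

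**Conclusion.** The point holds as an inconsistency that limits what the study may conclude. As designed, it can report swab-evoked pain ratings and their association with temperature. It cannot report a pain threshold, a pressure value or an objective measure of pain. This follows from reading 12.1 B and 12.2 against the title, 4.1 and 19.1, and needs no assumption.

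The consequence for the endpoint is real in direction but unknown in size. Uncontrolled force adds error to the marking of sensitive areas, and a difference in examiner or technique between groups could bias it. The shrinkage to 71%, 84% or 95% rests on assumed reliabilities and independent random error; the false-positive rates rest on an assumed shift. None of these is an estimate for this study. Pilot status excuses the missing power analysis but not the mismatch between label and measure.

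**What to change.** 1. In the title, 2.1, 4.1 and 19.1, replace *objective*, *thresholds* and *pressure* with *swab-evoked pain rating (0-10)*. Where 2.1 and 4.1 describe the wider technique, say that this stage does not measure force. Limit conclusions to the association between these ratings and temperature.
2. In 12.1 B, have the same existing examiner test every case and control at the same loci in one fixed order, and record the number of applications per locus.
3. In 19.1, state that examiner force is unmeasured, so a weak association between temperature and pain cannot be read as absence of a link.

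**Cost.** Wording changes, one extra recorded item and scheduling around one examiner; no new equipment or staff. One examiner removes differences between examiners, but not the possibility that this person presses differently in cases and controls. Item 3 covers that remainder.

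**Optional, and not part of the low-cost change.** A repeat pass would estimate within-visit repeatability, but only within one examiner, and without a force measure it could not separate force from sensitivity. It would add a research-only painful stimulus, so the risk text in 23.1 and the consent text would need review. If women could decline it, the most sensitive might be lost from the estimate.

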3.0 Scientific Endpoints*

3.1 *Describe the scientific endpoint(s), the main result or occurrence under study.*

NOTE: Scientific endpoints are outcomes defined before the study begins to determine whether the objectives of the study have been met and to draw conclusions from the data. Include primary and secondary endpoints. Some example endpoints are: reduction of symptoms, improvement in quality of life, or survival. Your response should not be a date.

Response:

Thermographic evidence of inflammation in the areas of pain sensitivity in women with provoked vulvodynia compared to normal controls.

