13.0 Study Timelines*

13.1 Describe the anticipated duration needed to enroll all study subjects.

Response: Two years

13.2 Describe the duration of an individual subject's participation in the study. Include length of study visits, and overall study follow-up time.

Response: Participant will only have one study visit lasting from 30-60 minutes.

13.3 Describe the estimated duration for the investigators to complete this study (i.e. all data is collected and all analyses have been completed).

Response: Three years

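### The swab procedure does not require touch order to be varied or recorded, so if one sequence is used for all women, drift over successive touches cannot be separated from location in the pain map.

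*Combined protocol and SAP*

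**What the plan says.** The primary objective in section 1.0 (Study Summary) concerns location: "Develop annotated pain maps showing region and size of area sensitive to mechanical stimulus". The hypothesis in section 2.2 also concerns pattern, "Women with vulvodynia will show specific patterns of pain sensitivity and inflammatory changes", and sets it against women without vulvar pain.

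The pain measurement is given in one sentence of section 12.1 B: "Subjective pain at several predetermined loci will be assessed with a cotton swab", with each rating given on a 0-10 scale. The ratings are then added to the thermographic map. The number of loci, the order of touches, the interval between them and any repeats are not stated. Section 12.2 lists the swab ratings among the data to be collected, but no touch number. Section 19.1 describes no locus analysis and no term for order.

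Three other statements bear on the point:

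- Section 4.1 says of the swab test: "This has been the standard of care for many years, but reproducibility has not been assessed".
- Section 13.2 says: "Participant will only have one study visit lasting from 30-60 minutes".
- Section 12.1 A places the infrared imaging before any contact with the vulva other than the drape.

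Section 12.3 refers to an attached data collection form, which is not in the text available for this review.

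**The concern.** Ratings taken one after another on tender tissue may not be independent of their place in the sequence. They may climb as the tissue sensitises, or fall as the woman habituates. An examiner with a list of predetermined sites may well work through it the same way each time. Locus and touch number would then be one variable: the site touched last would carry the accumulated drift in every woman, and the map would show it as anatomy.

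The within-woman location pattern is the primary objective. It also feeds the database in which pattern-finding by artificial intelligence is planned (section 1.0, secondary objective b). Once data have been collected in a single common order, no later analysis can remove the ambiguity, and the one-visit design provides no second rating to check it.

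**Working it through.** **No figure to reproduce.** Section 19.2 states that no power analysis will be performed, and the documents give no SD, alpha or number of loci. The only input from the documents is 30 cases (section 1.0: 60 women, 30 per group). The rest are assumptions, shown over a range:

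- loci K = 5 or 8 (section 12.1 B says only that there are several)
- linear drift b = 0.1, 0.2 or 0.3 points per touch on the 0-10 scale
- within-woman SD of a single rating s = 1.5 or 2.5
- no true difference between loci; two-sided 5% paired t-test of last against first locus

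**Step 1: can order and location be separated?** Take a model with K locus indicators plus touch number, which has K + 1 columns. If the order is the same in all 30 women, touch number is a fixed function of locus. The design then has rank 5 of 6 (K = 5) or 8 of 9 (K = 8), so locus and drift effects are not separately estimable. If the order is randomised per woman and recorded, the rank is full: 6 of 6 and 9 of 9.

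**Step 2: size of the false difference under a common order.** The last locus is K − 1 touches after the first, so the false difference is (K − 1) × b.

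- K = 5: 4 × 0.1 = 0.4; 4 × 0.2 = 0.8; 4 × 0.3 = 1.2 points
- K = 8: 7 × 0.1 = 0.7; 7 × 0.2 = 1.4; 7 × 0.3 = 2.1 points

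**Step 3: how often it would be called significant.** The standard error of the mean paired difference is s × √(2/30), which is 0.387 for s = 1.5 and 0.645 for s = 2.5. Rejection rates follow from the noncentral t distribution with 29 degrees of freedom and noncentrality equal to the false difference divided by its standard error.

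| Loci | SD | b = 0.1 | b = 0.2 | b = 0.3 |
|---|---|---|---|---|
| 5 | 1.5 | 17% | 51% | 85% |
| 5 | 2.5 | 9% | 22% | 44% |
| 8 | 1.5 | 42% | 94% | over 99% |
| 8 | 2.5 | 18% | 55% | 88% |

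With b = 0 the rate is 5%. In simulation (4,000 studies per setting) with the order randomised per woman, the mean false difference is about zero and the rejection rate stays at about 5% whatever the drift.

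**Step 4: the case-control comparison.** With a common order, the group difference in the last-minus-first contrast is biased by (K − 1) × (drift in cases − drift in controls). Equal drift gives zero. If drift differs by 0.25 points per touch, the bias is 4 × 0.25 = 1.0 point with 5 loci, or 7 × 0.25 = 1.75 points with 8.

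**Step 5: the thermographic endpoint.** The images precede the swab, so touch order cannot alter them. The endpoint in section 3.1 reads: "Thermographic evidence of inflammation in the areas of pain sensitivity in women with provoked vulvodynia compared to normal controls". Order can reach it only through how those areas are defined, if the swab ratings define them.

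**The case against.** A reader might infer that the protocol prescribes a single pass in one fixed order and that the map will therefore be an artefact. The documents do not support this. Predetermined loci fix where touches are made, not their sequence or number, and the data collection form cited in section 12.3, which might give an order, could not be seen. Bias requires both a sequence common to all women and real drift, and the documents establish neither. If examiners vary the order haphazardly, the main effect is added noise, although bias is possible if the order follows the woman's complaint.

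The controls also matter. The hypothesis is comparative, and drift shared by both groups cancels. This stands, but only for that comparison. It does not protect the within-woman map, and the documents give no reason to assume equal drift in women with and without provoked pain.

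The magnitudes can be challenged too. Number of loci, SD and drift are all assumed. First against last is the contrast most affected by linear drift. Section 19.1 plans no such test, and a shift in mean rating need not change the mapped region or its size. All of this stands, so the figures show what could happen and are not forecasts.

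Finally, this is a self-described pilot built on a routine examination. That limits the severity. It does not remove the point, because the pilot's data are meant to support diagnostic metrics (section 19.1) and order cannot be varied after collection.

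**Conclusion.** The point holds conditionally. The protocol neither requires touch order to be varied nor asks for it to be recorded. If the sequence is common to all women, drift and location are fully confounded within women, and that affects the primary objective directly.

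Over the assumed ranges, the false first-versus-last difference runs from 0.4 to 2.1 points on the 0-10 scale and would be significant in about 9% to over 99% of 30-case studies. That spread reflects how little the documents fix. If there is no drift, there is no bias. Absence of drift cannot be taken for granted, since section 4.1 concedes that the test's reproducibility is unassessed.

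The case-control comparison is biased only by drift that differs between groups, and the infrared images not at all. This is a worthwhile, inexpensive improvement to make before data collection. It does not show that the planned maps are invalid.

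**What to change.** 1. In section 12.1 B, state the loci and print a computer-generated random (or counterbalanced) order of them on each woman's data form.
2. Add touch number at each locus to the section 12.2 list. This helps only if the order varies; under a fixed order it repeats the locus label.
3. In section 19.1, specify the locus analysis and include touch number as a term. Randomisation removes the systematic artefact from the average map. An individual woman's map still carries her own drift, which the term adjusts for on average.
4. The documents mention no outer-to-inner sequence. If one is kept for clinical reasons, state that inner-versus-outer differences remain confounded with touch order. Randomise within each ring and limit order-free conclusions to loci within a ring.
5. If the data collection form already sets an order, bring it into section 12.1 B so that the procedure can be replicated.

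The cost is one randomised list per form and one extra recorded field. The examiner must also follow the sheet rather than habit in what is otherwise a routine examination. Sample size, visit and imaging are unchanged.
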